concerns with the supplementation and to ensure that their depression did not worsen (and it did not). Women were then seen at three months for follow-up measures and for prescription refill. For all 3 time points, patients completed questionnaires that included: depression (CES-D) and diabetes self-management which included diabetes self-care inventory (SCI) and diabetes distress using the Problem Areas in Diabetes Scale (PAIDS). For the pilot study, labs and physical measurements were also assessed and included vitamin D, calcium, PTH, HbA1c, blood pressure, and weight. Depression was verified at baseline using the Diagnostic Interview Schedule (DIS). Following completion of the study, all patients were given their labs and referred to their healthcare provider for future follow-up.

Repeated measures ANOVA results indicated that depression symptoms decreased significantly over time. In addition, there was a significant improvement in self-care behaviors and less diabetes distress. Vitamin D levels increased to a therapeutic level, and there were no significant changes in labs (calcium and parathyroid hormone). Although there was no improvement in HBA1c, the average baseline value indicated very good control (<7%). Other investigators have reported no change in HBA1c with vitamin D supplementation (97-98). A clinically and statistically significant decrease in systolic blood pressure was observed. There was also a small decrease in weight.

Variables	Baseline Mean (SD)	Three Months Mean (SD)	Six Months Mean (SD)	P value
Depression-CES-D	26.83 (7.6)	15.13 (8.9)	12.15 (8.3)	<.001
Self Care (SCI)	2.76 (.58)	2.87 (.57)	2.88 (.64)	.041
Distress (PAIDS)	29.00 (14.2)	21.29 (14.4)	19.36 (14.9)	.001
Vitamin D (ng/ml)	18.78 (7.0)	34.39 (9.4)	37.5 (9.5)	<.001
Systolic BP (mmHG)	140.43 (17.1)	135.04 (17.1)	132.46 (14.3)	.007
Weight (pounds)	226.10(59.0)	224.64 (59.9)	223.58 (59.4)	.026

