Hypothesis 1: Women receiving 50,000 IUs vitamin D supplementation will report fewer depressive symptoms (primary outcome), increased diabetes self-management mediated by depression improvement (secondary outcome), and have a lower systolic BP (exploratory) compared to those 5000 IUs at three and six months follow-up.

For analysis of the primary outcome (depressive symptoms) generalized, linear, mixed models (GLMM) for repeated measures will be used (154). The proposed model will have one between-subjects variable GROUP (vitamin D supplementation; control) with two levels and one within-subjects variable TIME with three levels (baseline, 3 and 6 months). The test of the hypotheses will hinge on the GROUP by TIME interaction as an indication of group differences in the variable of interest over time. A given hypothesis will be supported with the finding of a statistically significant GROUP by TIME interaction, and the finding that the means are in the hypothesized direction. GLMM will be implemented using SPSS which will provide estimates of the means for each outcome variable by time and treatment groups. The results will be summarized with adjusted means and 95% confidence intervals. A compound symmetric covariance structure will be assumed. If necessary, other covariance structures, such as Huynh-Feldt, will be investigated. An intention-to-treat analysis (ITT) which includes an analysis of completers and noncompleters will also be done using GLMM. Stratification by depression severity should provide comparable groups at baseline; however, differences will be assessed. All analyses will control for baseline values of body composition (body fat), race (white compared with nonwhite), and time at entry into the study (as season of the year, winter, summer, spring, fall) as previously done by our consultant, [name], in his vitamin D trials. Other covariates, related to diabetes (length of time with diabetes, HBA1c), lifestyle factors, (physical activity, diet), and previous depression will be added to generate a multivariate model which is parsimonious and based on the clinical relevance and statistical significance of these factors.

For analysis of the secondary outcome (self-management), regression analysis will be used to test whether an improvement in self-management is mediated by an improvement in depressive symptoms (Figure). The Preacher and Hayes macro add-on for SPSS will be used. This technique estimates the path coefficients and

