generates bootstrap confidence intervals for total and specific indirect effects of the independent variable (vitamin D supplementation) on the dependent variable (diabetes self-management) through one or more mediator variables (depressive symptoms). This method allows for testing indirect effects through a mediating variable without the estimation of a direct link between independent variable on an outcome, and also adjusts for the potential influence of covariates (155, 156).

For the exploratory outcome (blood pressure), GLMM will be used to examine for the direct effect of vitamin D on blood pressure since there is physiologic evidence to support this. The GLMM statistical procedures described above will be used.

Hypothesis 2: Women receiving 50,000 IUs vitamin D supplementation will have a decrease in inflammatory biomarkers which will be associated with fewer depressive symptoms compared to 5000 IUs at three and six months follow-up.

For this exploratory hypothesis, to determine if there is a decrease in the inflammatory markers, the same procedures (GLMM) will be used. If significant, then correlational methods (parametric and non-parametric) will be used to explore the association between vitamin D supplementation, depression, and the inflammatory biomarkers.

1. For the sub-study FAMDD, the qualitative component (**Aim 1**) interview data is being transcribed.

Following transcription, there will be verification of the transcription by [name]. Once these data have been verified, a narrative analysis will be conducted. Narrative inquiry was chosen to focus on the relationship between individuals' life stories and it guides synthesis of data to represent the participants' stories as a whole. Particular modifiable factors that mitigate health risks for family members and factors that facilitate self-management will be identified. Study team involved in this component of qualitative analysis includes [name], [name], [name] and [name].

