d. Sample Size Estimation. Based on our power estimates, a sample of 75 women per group will be needed for a final sample of 150 women. We have planned for a conservative attrition (15%) which is higher than our Sunshine pilot (8%) but consistent with our SWEEP trial (59). **Therefore, 180 (90 per group) will be enrolled into the treatment arms.** Thus far, out of 169 patients enrolled, only 83 (49%) have been randomized to treatment arms. Thus, we will enroll 360 as we have had a screen failure of almost 50% to allow for a sufficient number of persons to be randomized. For the power analysis, we used a repeated measures approach formulae developed by Hedeker et al. (158) which allows comparisons of the group means across time while adjusting for baseline values and accounting for the correlation between baseline and follow-up observations. We have assumed a 2 tailed test with a type I error rate of 0.05 for each outcome. **Depression:** There was a 14 point decrease in depression from baseline to 6 months following vitamin D supplementation using the CES-D (see pilot data). Using the control group in the SWEEP study (which had the same enrollment criteria for depression and did not receive treatment), there was a 7 point decrease in depression (28.8 to 21.4) as depression symptoms can improve without treatment. Given these group difference, the effect size is .46. A sample size of 30 per group would provide 95% power. We also powered for depression remission (CED-D < 16) as other depression trials (159). In our vitamin D study, 55% of women had remission of their depression at 3 months and 63% at 6 months. Using the control group data from the SWEEP study, 30% had remission of depression at 3 months and 20% at 6 months. Having this information, a sample size of 75 per group (n=150) would be needed to detect differences in depression remission at 3 months and a sample of 25 per group (n=50) to see the difference at 6 months. **Diabetes Self-Management:** There were significant differences from baseline to six months (see pilot data) to calculate the effect sizes. We calculated an effect size of .70 for diabetes distress and .33 for self-care. For diabetes self-efficacy, an effect size of .30 based on our previous research (SWEEP) will be used. A sample of 75 per group (n=150) will achieve 85% power on these study outcomes. **Blood Pressure:** We observed a decrease of 8 mmHg in the vitamin D study but no change in a control group from the SWEEP study (136.2 mmHg to 135.9 mmHg). Pfeifer et al. (96) reported a 7% decrease in blood pressure in women after 800 IUs of D₃ for 6 weeks. To be conservative, we will assume a difference of about 5 mmHg to account for the placebo effect and regression to the mean phenomena commonly observed in clinical trials. This difference yields an effect size of about 0.3. A final sample of 150 (75 per group) would provide 80% power to assess this outcome. **Inflammation (Exploratory):** Using pilot data of [name] (see pilot data) a sample size of 75 per group provides 85% power to detect differences between groups on depression and inflammation. **For the meditational analyses,** power was estimated using effect sizes from our previous research and current pilot study. Although the depression effect sizes discussed above are large (160), a more conservative approach anticipating medium effect sizes was employed for the mediation analysis. With medium effects for self-care outcomes, a total sample of 135 would achieve 95% power.

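### Blood pressure is said to have 80% power with no correlation or contrast stated; the written GROUP by TIME rule reaches that figure only if the correlation is near .77.

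*Combined protocol and SAP*

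**What the plan says.** Section V.5.d (Sample Size Estimation) bases its power figures on a cited repeated-measures formula described as "adjusting for baseline values and accounting for the correlation between baseline and follow-up observations". The error rate is common to all outcomes: "We have assumed a 2 tailed test with a type I error rate of 0.05 for each outcome". For blood pressure it continues: "To be conservative, we will assume a difference of about 5 mmHg", then "This difference yields an effect size of about 0.3", then "A final sample of 150 (75 per group) would provide 80% power to assess this outcome". No correlation is given, and the section does not say which contrast among visits the 80% refers to.

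Section V.5.b (Data Analysis) gives the decision rule. TIME has three levels, one of which is baseline, and compound symmetry is assumed. "The test of the hypotheses will hinge on the GROUP by TIME interaction": a hypothesis counts as supported if that interaction is significant and the means lie in the expected direction. The baseline covariates that are always included are body fat, race and season; baseline blood pressure enters as an outcome level, not as a covariate. For blood pressure, labelled exploratory, the section says: "The GLMM statistical procedures described above will be used".

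**The concern.** The power statement and the decision rule describe different statistics. Section V.5.d describes a comparison of arms adjusted for baseline, with one effect size. Section V.5.b describes an omnibus test of whether the arm difference varies over three visits: with two arms and three visits, (2 − 1) × (3 − 1) = 2 numerator degrees of freedom. If both arms start level and the difference is already present at 3 months and stays constant, the omnibus test spends a degree of freedom on a pattern that is not there. It also uses baseline less efficiently than covariate adjustment does.

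At stake is how a non-significant blood pressure result is read. Lower systolic pressure is part of the Aim 1 hypothesis. A reader who trusts the printed 80% would take a non-significant interaction as fair evidence against a 5 mmHg difference, when the chance of detecting that difference could be nearer one half.

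**Working it through.** **Inputs.** From V.5.d: 75 per arm, two-sided 5%, difference about 5 mmHg, effect about 0.3 SD (5/17.1 = 0.29 with the pilot baseline SD). From V.5.b: three time levels and compound symmetry. From the section IV pilot table: systolic means (SD) of 140.43 (17.1), 135.04 (17.1) and 132.46 (14.3), p = .007 by repeated-measures ANOVA; 46 women were retained at 6 months. Assumed here because the plan does not say: equal arm means at baseline and the full 0.3 SD at both 3 and 6 months.

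**Can the 80% be reproduced?** An unadjusted two-sample comparison at one visit has about 45%, so it is not that. A 1-df contrast of the 3- and 6-month mean, adjusted for baseline, has noncentrality

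λ₁ = (n/2) × 0.3² / [(1 + r)/2 − r²], on F(1, 146).

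At r = .62: 37.5 × 0.09 / (0.81 − 0.3844) = 3.375/0.4256 = 7.93, power 80%. So the printed figure fits this contrast at r of about .62, a value that the documents do not contain.

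**The written rule.** Arm differences over the three visits are (0, 0.3, 0.3), with mean 0.2. The squared deviations sum to 0.04 + 0.01 + 0.01 = 0.06. Then

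λ₂ = (n/2) × 0.06 / (1 − r) = 2.25 / (1 − r), on F(2, 296).

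**Correlation implied by the pilot table.**
- p = .007 on (2, 90) df corresponds to F = 5.25.
- The mean of the three means is 135.98; the squared deviations sum to 19.83 + 0.88 + 12.37 = 33.08.
- MS(time) = 46 × 33.08 / 2 = 761, so MSE = 761/5.25 = 145.
- The average variance is (17.1² + 17.1² + 14.3²)/3 = 263.
- r = 1 − 145/263 = .45.

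This assumes n = 46, an uncorrected F test and compound symmetry. With n = 50, r is about .40.

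**Results (75 per arm, 0.3 SD at both follow-ups).**

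| r | λ₂ | 2-df interaction | λ₁ | 1-df adjusted contrast | Difference (points) |
|---|---|---|---|---|---|
| .40 | 3.75 | 39% | 6.25 | 70% | 31 |
| .45 | 4.09 | 42% | 6.46 | 71% | 29 |
| .50 | 4.50 | 46% | 6.75 | 73% | 27 |
| .60 | 5.63 | 55% | 7.67 | 79% | 24 |
| .62 | 5.92 | 57% | 7.93 | 80% | 23 |
| .70 | 7.50 | 68% | 9.37 | 86% | 18 |
| .77 | 9.78 | 80% | 11.55 | 92% | 12 |

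A simulation of 20,000 trials at r = .449 gave 42.1% for the interaction and 71.2% for the contrast. At that correlation the interaction would need about 178 per arm for 80%.

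**Sensitivity at r = .45.**
- With 5/17.1 = 0.29 SD, the interaction has 40%.
- With 5 mmHg and the pilot's three unequal SDs (r about .45), the figures are 42% for the interaction and 77% for the contrast.
- With 0.2 SD at 3 months and 0.3 SD at 6 months: 34% and 56%.
- With 0.05 then 0.3 SD: 37% and 31%. With 0 then 0.3 SD: 42% and 24%. In these last two cases the interaction is the stronger test.

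**Primary outcome.** The planned CES-D difference is 7 points. Even with the largest pilot SD (8.9) that is 0.79 SD, and λ₂ at r = .45 is 37.5 × (2/3) × 0.79² / 0.55 = 28.4, giving power above 99%.

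**The case against.** The strongest reply is that the 80% does not identify any test. With the correlation free, it can be reached by baseline-adjusted analysis at one visit (r = .755), by mean change (r = .713), by change at one visit (r = .785), or by the written interaction itself (r near .77). This stands. A reader might infer that V.5.d sized the averaged 1-df contrast and that its arithmetic is wrong. The section names no contrast and its cited method is not reproduced, so neither inference is proven. What is shown is that the figure cannot be checked and that the written rule delivers it only at a high correlation.

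Second, r = .45 is fragile. It is solved from a rounded p value, under assumptions about n and the covariance, in a one-arm pilot. This trial also excludes baseline systolic pressure above 160 mmHg, a limit not among the pilot criteria listed in section IV. That is fair, and it is why a range is given; the interaction stays below 80% for any r below about .77.

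Third, the averaged contrast is not uniformly better. It loses power if the effect builds, and it is the weaker test if the effect appears almost only at 6 months. The plan does not state the time course expected for blood pressure. This also stands, and the fix should say so.

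Fourth, blood pressure is exploratory, 75 per arm is also required for 3-month remission, and V.5.b already promises adjusted means with 95% confidence intervals. These points limit the consequence, but they do not make the printed power correct for the written rule.

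**Conclusion.** The point holds in limited form. With 0.3 SD at both follow-ups and compound symmetry, the rule that decides blood pressure has about 42% power at the pilot-implied r = .45 (39% to 42% for r from .40 to .45), 55% at .60 and 68% at .70. The plan prints 80%.

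Two stronger readings are tempting and should be avoided. One is that the choice of test takes power from 80% down to 42%. Those two figures belong to different correlations: 80% fits the 1-df contrast near r = .62, whereas 42% is the interaction at r = .45. Like for like, it is 71% against 42% at r = .45, or 80% against 57% at r = .62. At r = .45, therefore, about 29 of the 38 points come from the test and about 9 from the correlation. The other is that a true 5 mmHg difference would more likely than not be missed. That is so only below r of about .55.

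The point is confined to an exploratory outcome. It should be corrected because the plan claims a property that its written test has only at a correlation well above the one its own pilot table implies.

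**What to change.** In V.5.d, state the correlation assumed for systolic blood pressure, and its source, and restate the power for the test that will be used. If the interaction remains the deciding test, print about 42% to 68% for r from .45 to .70.

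Preferably, change V.5.b so that blood pressure is decided by one pre-specified 1-df contrast: the arm difference averaged over 3 and 6 months, with baseline systolic pressure as a covariate. Keep GROUP by TIME as supportive. V.5.d would then state about 71% at r = .45 and 79% at r = .60. The text should name the trade-off: at r = .45 the averaged contrast falls to about 56% if the effect is 0.2 SD at 3 months and 0.3 SD at 6 months, and it is weaker than the interaction if the effect appears almost only at 6 months. The choice should be fixed before unblinded data are seen.

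The cost is a few sentences and one restated power figure. It needs no more participants, visits or data.

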Given our preliminary data, we hypothesize a significant decrease in depression symptoms, improved diabetes self-management, and a lowering of systolic blood pressure in the treatment group (vitamin D) compared to the control group using a RCT. In our proposed study, we will measure weight since it can impact on both blood pressure and vitamin D levels (102). Since vitamin D levels could be affected by external factors such as sun exposure and dietary intake (27, 115, 116), we measured these as well. Women reported an average of 10% body exposure to the sun (largely their head and upper forearm) with no change over time in our pilot study. Dietary intake of vitamin D was low (153 IUs/ day), but given the limited natural food sources for vitamin D, this finding was not surprising. Since other research has addressed these factors, we will continue to measure these factors and address them in the data analysis.

Pilot work on depression and inflammation. [name], co-investigator and psychiatrist, has studied depression and inflammation but not vitamin D. His study of 48 patients with major depressive disorder (MDD assessed by DSM IV criteria) and 23 healthy controls (HC) were compared for pro-inflammatory cytokines (IL-6, TNF α) and hs CRP using a compact biochip array system (Randox Technologies; Evidence Investigator TM). Depressed patients demonstrated significantly higher levels of inflammation than healthy controls as reflected in plasma levels of TNF- α (MDD 2.15+/- 0.04 pg/ml and HC 1.59+/-1.59 pg/ml, p=0.05) as well as plasma IL-6 (MDD 0.810 +/- 0.012 and HC 0.665+/- 0.023 pg/ml, p=0.05). Similarly, hs-CRP in depressed individuals was significantly higher than in healthy control subjects (MDD 3.53 +/-0.4 mg/l; HC 1.79 +/- 0.7 mg/l, p<0.05). Given [name] success in measuring inflammatory biomarkers in depressed patients, we have proposed exploration of these measures following treatment with vitamin D supplementation where we hypothesize women will have a significant improvement in depressive symptoms.

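### The stated 85% power for inflammation is not supported for a 50,000 versus 5000 IU comparison, because its only source is a depressed-versus-healthy contrast without vitamin D

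*Combined protocol and SAP*

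**What the plan says.** Section V.5.d (Sample Size Estimation) sets the general rule: "We have assumed a 2 tailed test with a type I error rate of 0.05 for each outcome". It names a repeated-measures formula that adjusts for baseline and uses the correlation between baseline and follow-up. For inflammation, labelled exploratory, it refers to the pilot data and states that "a sample size of 75 per group provides 85% power to detect differences between groups on depression and inflammation". It gives no marker, standard deviation, effect size or correlation for this figure.

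The pilot data are in section IV, under the pilot work on depression and inflammation. The co-investigator "has studied depression and inflammation but not vitamin D". The design is described as follows: "His study of 48 patients with major depressive disorder (MDD assessed by DSM IV criteria) and 23 healthy controls (HC) were compared". Two of the three markers are printed as "MDD 2.15+/- 0.04 pg/ml and HC 1.59+/-1.59 pg/ml, p=0.05" for TNF-alpha and "plasma IL-6 (MDD 0.810 +/- 0.012 and HC 0.665+/- 0.023 pg/ml, p=0.05" for IL-6. For hs-CRP the figures are 3.53 +/- 0.4 against 1.79 +/- 0.7 mg/l, with p below 0.05. Whether +/- means a standard deviation or a standard error is not stated.

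The trial itself (sections V.1, V.2 and VI.A) enrols women with type 2 diabetes and elevated depressive symptoms and randomises them to 50,000 or 5000 IU weekly. In section V.5.b, Hypothesis 2 tests the biomarkers with the mixed model. It goes on to correlational work with depression only if that test is significant.

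**The concern.** A power statement needs an effect size for the comparison that will be tested. Here that is the difference in a marker between two vitamin D doses, in women who all have depressive symptoms. The pilot supplies a different quantity: how far depressed patients lie from healthy people, with no treatment given. Even a fully effective dose need not move a marker by that amount relative to the low dose, and nothing in the documents says what share to expect.

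Aim 2 is the mechanistic aim, and its second step depends on a significant first step. A stated 85% could lead a reader to take a null biomarker result as evidence against the mechanism. That reading would rest on a figure that does not describe the trial's comparison.

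**Working it through.** **Inputs.** Two-sided alpha 0.05 and 75 per group (V.5.d). Pilot sizes 48 and 23, with the means, spreads and p-values from section IV. The correlation of 0.3 to 0.7 is an assumption, because the documents give none.

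**1. Reproducing the 85%.** Two routes come close (two-sample t test, 75 per group).

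- From the printed p=0.05: d = t(0.975, 69 df) x sqrt(1/48 + 1/23) = 1.995 x 0.2536 = 0.506. Power is 86.8%.
- From TNF-alpha with +/- read as SD: equal-weight SD = sqrt((0.04² + 1.59²)/2) = 1.125, and d = (2.15 - 1.59)/1.125 = 0.498. Power is 85.8%.

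The difference needed for exactly 85% is d = 0.4925. Both routes therefore use essentially the whole case-control gap as the between-dose effect (0.4925/0.506 = 97%; 0.4925/0.498 = 99%).

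**2. Other readings of the same figures.** These do not lead to 85%.

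| Marker and reading | Full-gap d | Share of gap needed for 85% |
|---|---|---|
| TNF-alpha, SD, n-weighted | 0.62 | 79% |
| TNF-alpha, SE | 0.10 to 0.13 | more than the full gap |
| IL-6, SD | 7.9 to 8.9 | about 6% |
| IL-6, SE | 1.49 to 1.57 | 31% to 33% |
| hs-CRP, SD | 3.1 to 3.4 | 15% to 16% |
| hs-CRP, SE | 0.57 to 0.59 | 83% to 87% |

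**3. Consistency of the pilot figures.** For IL-6, with +/- taken as a standard error (the reading that gives the smaller statistic), z = (0.810 - 0.665)/sqrt(0.012² + 0.023²) = 0.145/0.0259 = 5.6. That conflicts with a printed p=0.05. For TNF-alpha, the healthy-control spread equals its mean (1.59 and 1.59), beside a spread of 0.04 in patients.

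**4. Power at half the gap, d = 0.506/2 = 0.253.**

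- Unadjusted test at one time point: 34%.
- Baseline-adjusted, mean of two follow-ups, equal correlation r between all visits: the variance factor is (1 + r)/2 - r². It is 0.56 at r = 0.3 and 0.36 at r = 0.7. The effective d is 0.253/sqrt(0.56) = 0.338, giving 54% power, and 0.253/sqrt(0.36) = 0.422, giving 73%.

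**5. Detectable difference with 75 per group.**

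- Unadjusted, one time point: 0.49 at 85% power and 0.46 at 80%.
- Baseline-adjusted, two follow-ups averaged, 85% power: 0.4925 x sqrt(0.56) = 0.37 at r = 0.3, and 0.4925 x sqrt(0.36) = 0.30 at r = 0.7. These are 73% and 58% of a 0.506 gap.

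**The case against.** A reader might infer that the 85% holds only if the high dose removes the whole gap between depressed and healthy people. The documents do not support that. The power paragraph names no marker or effect size, so the full-gap reading is a reconstruction from a near match. As printed, IL-6 would need at most about a third of its gap, and hs-CRP 15% to 87% of its gap.

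The reconstruction also leans on a p-value that the IL-6 figures contradict, and p=0.05 may be a rounded or threshold value. The value 0.506 is thus only a working figure for showing sensitivity.

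A reader might also infer from the 34% that the trial has low power for any partial effect. That figure belongs to an unadjusted test at one visit, whereas the plan names a baseline-adjusted repeated-measures method. Under that method, with the assumed correlations, 58% to 73% of a 0.506 gap is enough for 85%.

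On materiality, the aim is exploratory, 75 per group is required separately by 3-month remission, and adjusted means with 95% confidence intervals are already planned. These points limit the consequence. None of them supplies a between-dose effect, so the lack of support for the 85% stands.

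**Conclusion.** The concern holds as a matter of support: the 85% rests on a contrast that the trial does not contain, and no between-dose marker effect stands behind it. It is not an arithmetic error, since about 85% can be reproduced from the pilot figures in two ways.

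The size depends on what is assumed. If the working gap is d = 0.506 and the doses differ by half of it, power is about 34% unadjusted at one visit. It is about 54% to 73% under baseline adjustment with two averaged follow-ups and a correlation of 0.3 to 0.7. Both are below 85%. The correlation, the equal-correlation structure and the half share are assumptions, not figures from the documents. The inconsistencies in the pilot figures are a further reason not to rest any power claim on them as printed. The matter affects how Aim 2 is interpreted, not the design or the enrolment target.

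**What to change.** In V.5.d, delete the 85% claim for inflammation and state that no estimate of a between-dose effect on the markers was available. In its place, give what 75 per arm can detect, with the test named:

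- a between-arm standardised difference of about 0.49 with 85% power, or 0.46 with 80%, in an unadjusted single-time-point test;
- about 0.30 to 0.37 with 85% power under the baseline-adjusted repeated-measures method with two follow-ups averaged, if the correlation is 0.3 to 0.7, marked as assumed.

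Add that Aim 2 biomarker results will be interpreted from the between-arm estimates and their 95% confidence intervals, not from a stated power. In section IV, check the IL-6 and TNF-alpha entries against the source and say whether +/- is SD or SE.

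The cost is a few sentences and a less favourable statement for an exploratory aim. The sample size and the planned models stay as they are.
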